2.3.2 Safety population

The safety population consists of all randomized patients who receive at least 1 dose of open-label IMP (regardless of the amount of treatment administered). Patients will be analyzed for safety analyses according to the treatment actually received.

In addition:

- Nonrandomized but treated patients will not be part of the safety population; however, their safety data will be presented separately;
- Randomized patients for whom it is unclear whether they took the IMP will be included in the safety population as randomized;
- When a patient is exposed to both FRC and GLP-1 receptor agonist, the patient will be analyzed in the treatment group (FRC or GLP-1 receptor agonist) in which he/she is treated longer;
- Patients will be excluded from the safety population only if there is documented evidence (ie, all study dates recorded as no medication taken) that patients have not taken the study medication.

2.3.3 Pharmacokinetic population

- For pharmacokinetic (PK) analyses, the PK population is defined as all randomized and treated patients who contribute with at least one valid plasma analysis of lixisenatide.

2.4 STATISTICAL METHODS

In general, descriptive statistics of quantitative efficacy and safety endpoints (result and change from baseline) by scheduled visit will be provided on observed cases (OC), ie, only including patients having a non-missing assessment at a specific visit.

Continuous data will be summarized by treatment group using the number of available observations (N), mean, SD, minimum, median, and maximum.

Categorical data will be summarized by treatment group using counts and percentages. Missing data will not be categorized in the summaries.

2.4.1 Demographics and baseline characteristics

No statistical test will be performed for the between-group difference on demographic and baseline characteristics (including medical history and baseline efficacy data).

Demographic and baseline disease characteristics, baseline efficacy variables and medical history and medical findings (see [Section 2.1.1](#)) will be summarized with appropriate descriptive statistics by treatment group and overall. Pathologies associated with past medical or surgical history will be summarized by primary SOC and HLT, with events sorted by primary SOC in internationally agreed order and decreasing frequency of HLT in the overall group. These summaries will be provided on randomized patients, using the treatment group to which they were randomized.

2.4.2 Prior or concomitant medications

Summaries of prior, concomitant and post-treatment medications will be presented on randomized patients for each treatment group (and overall for the summary of prior medications), using counts and percentages. No statistical test for the between-group difference will be performed.

Medications will be summarized according to the WHO-DD dictionary, considering the first digit of the anatomical therapeutic chemical (ATC) class (anatomic category) and the first 3 digits of the ATC class (therapeutic category). A given medication can be classified in several groups. All ATC codes corresponding to a medication will be summarized. Patients will be counted once in each ATC categories (anatomic or therapeutic) linked to the medication, therefore patients may be counted several times for the same medication.

The table for prior medications will be sorted by decreasing frequency of anatomic class followed by therapeutic class, based on the overall incidence across treatment groups. In case of equal frequency regarding anatomic classes (respectively therapeutic classes), alphabetical order will be used.

The tables for concomitant and post-treatment medications will be sorted by decreasing frequency of anatomic class followed by therapeutic class, based on the incidence in the FRC group. In case of equal frequency regarding anatomic classes (respectively therapeutic classes), alphabetical order will be used.

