8.2.3 Rescue Therapy

In case **HbA1c is above 8% at Week 12 or later on**, the Investigator will receive an alert issued by the central laboratory and should ensure that no reasonable explanation exists for insufficient glucose control and in particular that there is no intercurrent disease which may jeopardize glycemic control (eg, infectious disease), that the treatments are given at the planned dose and compliance to treatment and diet and lifestyle is appropriate. HbA1c assessment should be scheduled at next visit (if next visit is a phone call, it should be replaced by an unscheduled visit at site) or within 4 weeks. If appropriate corrective action fails and if the repeated HbA1c remain above 8%, a rescue therapy should be considered according to the Investigator's judgment.

In the FRC arm:

- rescue therapy is recommended only if further dose titration is not possible, ie, the patient is already at the maximum daily dose of 60 units;
- rapid acting insulin (insulin- glulisine when available) is suggested and should be started as a single daily administration to be given at the main meal of the day (excluding breakfast);
- basal insulin is not allowed in the FRC arm.

In the GLP-1 RA arm:

- suggested rescue therapy is basal insulin at the investigator's discretion.

During the extension period, suggested rescue therapy is rapid acting insulin (insulin- glulisine when available) for all patients.

All assessments planned at the end of the randomized treatment visit (V28) are to be performed before initiating rescue therapy during the randomized treatment period. All assessments planned at the end of extension period treatment visit (V35) are to be performed before initiating rescue therapy during the extension period. After these assessments are completed and rescue therapy initiated, the patient will remain in the study and continue to administer the study treatment (including background therapy). The planned visits and assessments should be performed until the last scheduled visit. Patients receiving rescue therapy during the randomized treatment period and eligible for the extension period can continue it as required.

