11.4.2 Prior and concomitant medications

All medications will be coded using the version of World Health Organization-Drug Dictionary (WHO-DD) currently in effect at Sanofi at the time of database lock.

Medications will be classified into the following three groups:

- Prior medications are those the patient took prior to the first injection of open-label IMP;
- Concomitant medications are those the patient continued or started on or after the first dose of open-label IMP up to 3 days after the last injection of daily IMP or 9 days after the last injection of weekly IMP);
- Post-treatment medications are those the patient continued or started on or after 4 days after the last injection of daily IMP or 10 days after the last injection of weekly IMP.

A given medication can be classified in several groups. Medications will be summarized according to the WHO-DD, considering the first digit of the ATC class (anatomic category) and the first three digits of the ATC class (therapeutic category). All ATC codes corresponding to a medication will be summarized, patients will be counted once in each ATC categories (anatomic or therapeutic) linked to the medication, therefore patients may be counted several time for the same medication.

Summaries of prior, concomitant and post-treatment medications will be presented on randomized patients for each treatment group (and overall for the summary of prior medications) using counts and percentages. No statistical test for the between-group difference will be performed.

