1 OVERVIEW AND INVESTIGATIONAL PLAN

1.1 STUDY DESIGN AND RANDOMIZATION

The study is an open-label, 1:1 randomized, active-controlled, 2-arm, 26-week treatment duration, parallel group multinational and multicenter Phase 3b study comparing

- Insulin glargine/lixisenatide fixed ratio combination (FRC) group;
- Glucagon-like peptide-1 (GLP-1) receptor agonist group.

At the end of the 26-week randomized treatment period, patients from the FRC group will be invited to participate in a 26-week single arm extension period.

The study comprises 4 periods (please see graph in [Section 1.4](#) and flowchart in [Appendix D](#)): (1) an up-to 2-week screening period; (2) a 26-week open-label randomized treatment period; (3) a 26-week single-arm extension period and (4) a post treatment safety follow-up period (patients who prematurely discontinue the study treatment will continue in the study up to the scheduled date of study completion).

At the end of screening period, eligible patients are centrally randomized (using permuted block randomization schedule) via IRT in a 1:1 ratio to 1 of the 2 treatment groups. The patients will be stratified by value of HbA1c at screening ($<8\%$, $\geq 8\%$) and GLP-1 receptor agonist subtype at screening (once (QD)/twice daily (BID) formulations, once weekly (QW) formulations).

It is planned to randomize a total of approximately 500 patients (250 patients per group).

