2.1.2 Prior or concomitant medications

All anti-diabetic medications taken within 6 months prior to the screening visit or during study are to be reported in the case report form pages. All other medications taken within 3 months prior to the screening visit or during study are to be reported in the case report form pages.

All medications will be coded using the version of World Health Organization-Drug Dictionary (WHO-DD) currently in effect at Sanofi at the time of database lock.

Medications will be classified into the following 3 groups:

- Prior medications are those the patient took prior to the first injection of open-label IMP. Prior medications can be discontinued before first IMP injection or can be ongoing during treatment period.
- Concomitant medications are those the patient continued or started on or after the first injection of open-label IMP up to 3 days after the last injection of daily IMP or 9 days after the last injection of weekly IMP.
- Post-treatment medications are those the patient continued or started on or after 4 days after the last injection of daily IMP or 10 days after the last injection of weekly IMP.

A given medication can be classified in several groups.

Any technical details related to computation, dates, imputation for missing dates are described in [Section 2.5](#).

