2.4.3.1 Extent of investigational medicinal product exposure

The extent of open-label IMP exposure will be assessed by the duration of IMP exposure during the study.

The duration of treatment exposure will be the total number of days of administration of the open-label IMP, regardless of unplanned intermittent discontinuations.

The duration of daily IMP exposure will be calculated as:

(Date of the last open-label IMP injection – Date of the first open-label IMP injection) + 1.

The duration of weekly IMP exposure will be calculated as:

(Date of the last open-label IMP injection – Date of the first open-label IMP injection) + 7.

Duration of IMP exposure (days) will be summarized using continuous descriptive statistics (N, mean, SD, minimum, median, and maximum). The cumulative exposure in patient years, defined as the sum of patients' duration of IMP exposure, will also be provided. In addition, duration of IMP exposure will be summarized categorically by counts and percentages for each of the following categories, and cumulatively according to these categories:

- 1 to 14 days,
 - 15 to 28 days,
 - 29 to 56 days,
 - 57 to 84 days,
 - 85 to 126 days,
 - 127 to 168 days,
 - 169 to 182 days,
 - 183 to 210 days,
 - 211 to 238 days,
 - 239 to 294 days,
 - 295 to 364 days
 - > 364 days.
- The exposure parameters are provided for the 26-week randomized treatment period and for the whole study treatment period (FRC group only), respectively.

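### The by-arm concomitant medication table has no Week 26 cut-off, so read literally it counts FRC extension patients for about twice as long as controls

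*SAP*

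**What the plan says.** SAP 2.1.2 counts drugs carried over from before treatment as well as new ones, within this window: "on or after the first injection of open-label IMP up to 3 days after the last injection of daily IMP or 9 days". The 9 days run from the final weekly injection. Protocol 11.4.2 sets the same window: "Concomitant medications are those the patient continued or started on or after the first dose of open-label IMP up to 3 days". There the 3 days run from the final daily injection, with 9 days for weekly products. Neither text mentions Week 26.

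SAP 2.4.2 then tabulates the result by randomized arm: "Summaries of prior, concomitant and post-treatment medications will be presented on randomized patients for each treatment group". The summary uses counts and percentages, each patient counts once per ATC category, and "No statistical test for the between-group difference will be performed". No period is named.

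The arms differ in how long they inject. Under SAP 1.1, "patients from the FRC group will be invited to participate in a 26-week single arm extension period". Protocol 6.1 keeps control patients out of the extension. The extension flow chart in Protocol 1.2 continues concomitant medication recording throughout.

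Other sections handle the unequal length explicitly. SAP 2.4.3.1 says of exposure: "The exposure parameters are provided for the 26-week randomized treatment period and for the whole study treatment period (FRC group only), respectively". Compliance (2.4.3.2), safety in general (2.4.5), hypoglycemia (2.4.5.1), adverse events (2.4.5.2) and laboratory data (2.4.5.4) are likewise divided into a 26-week part by arm and a later or whole-study part for FRC alone.

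**The concern.** A percentage of patients with a medication depends on how long they are watched. If one column covers about 52 weeks for most patients and the other 26, any class that patients start from time to time will look more common in the longer column.

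The trial is open-label, so readers will use this table to see whether co-medication was similar in the two arms over the 26 weeks being tested. A difference produced only by follow-up could be taken for a real imbalance, or could hide one.

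The pattern looks like an omission and not a choice. The change history in SAP 1.5 and 1.6 shows exposure, compliance, efficacy and safety summaries being revised when the extension was added. The recorded change to the medication definitions is for weekly formulations only.

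**Working it through.** The plan gives no figure for this table, so there is none to reproduce.

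**Inputs from the documents**
- Planned size: 250 per arm (SAP 1.3).
- FRC patients expected in the extension: about 230 (Protocol synopsis), a share f = 230/250 = 0.92.
- Lower value for f: the 20% drop-out assumption in SAP 1.3 leaves 250 × 0.8 = 200, so f = 0.80. Patients who stop FRC early cannot enter the extension, so both values are carried as a range.

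**Assumptions not in the documents**
- p is the chance that a patient not already using a class starts it within 26 weeks. It is taken from 2% to 30%.
- The start rate is constant and equal in the two arms.
- Early stopping within either period, and the 3- and 9-day tails, are ignored in the percentages.

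**Longest window**
- FRC in the extension: 364 + 3 = 367 days.
- Control, daily product: 182 + 3 = 185 days; ratio 367/185 = 1.98.
- Control, weekly product: 182 + 9 = 191 days; ratio 367/191 = 1.92.

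**Mean time at risk in FRC**
- f = 0.92: 0.92 × 52 + 0.08 × 26 = 49.9 weeks, 1.92 times control.
- f = 0.80: 0.80 × 52 + 0.20 × 26 = 46.8 weeks, 1.80 times control.

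**Expected percentages for a class with no baseline use**

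Control = p. FRC = f × [1 − (1 − p)²] + (1 − f) × p = p + f × p × (1 − p).

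For example, with p = 10% and f = 0.92: 0.10 + 0.92 × 0.10 × 0.90 = 0.1828.

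| Control | FRC, 200 enter | FRC, 230 enter | Ratio |
|---|---|---|---|
| 2% | 3.6% | 3.8% | 1.78 to 1.90 |
| 5% | 8.8% | 9.4% | 1.76 to 1.87 |
| 10% | 17.2% | 18.3% | 1.72 to 1.83 |
| 20% | 32.8% | 34.7% | 1.64 to 1.74 |
| 30% | 46.8% | 49.3% | 1.56 to 1.64 |

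**Classes already in use at baseline**

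The table counts continued as well as newly started drugs. If a share b of each arm is already on the class, control = b + (1 − b) × p, and FRC = b + (1 − b) × (the FRC value above). With p = 10% and 230 entering:
- b = 30%: 0.30 + 0.70 × 0.10 = 37.0% against 0.30 + 0.70 × 0.1828 = 42.8%, ratio 1.16.
- b = 60%: 0.60 + 0.40 × 0.10 = 64.0% against 0.60 + 0.40 × 0.1828 = 67.3%, ratio 1.05.

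**After a common Week 26 cut**

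Both arms have expectation p, and the excess is zero under equal rates.

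**The case against.** The strongest reply is that the period is unstated, not prescribed as 52 against 26 weeks. SAP 2.5.3 uses two last-injection dates for extension patients, one for the randomized period and one for the whole study, and 2.1.2 does not say which applies. SAP 3 bases the primary analysis of efficacy and safety on 26-week data. Appendix C, which the SAP contents list as a summary of analyses, was not in the text available for this review and might state a period. This stands as a limit on certainty. It does not remove the point: SAP 3 does not name the medication tables, and nothing in the available text applies a cut to them.

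Three stronger readings are tempting, and the documents do not support them.
- A reader might infer that rescue insulin started in the extension would distort the comparison of glucose-lowering therapy, since Protocol 8.2.3 says "During the extension period, suggested rescue therapy is rapid acting insulin". But need for rescue is a secondary endpoint restricted to the 26-week period (SAP 2.1.3.2). Its cumulative incidence is shown by arm for 26 weeks and for the whole study in FRC alone (SAP 2.4.4.2). That comparison does not depend on this table.
- A reader might infer that post-treatment medications are affected in the same way. Planned follow-up after the last injection is one contact at 3 or 9 days (Protocol 10.1.2.6 and 10.1.3.5). The calendar timing differs between arms, but completers in FRC gain no doubled time at risk.
- A reader might infer that at the first database lock the FRC window would vary with each patient's progress in the extension. That presumes extension data enter the first report, which no section says.

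The objection that the table is descriptive and untested is also right, and it limits the consequence.

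**Conclusion.** The point holds as a defect in how the period of one descriptive table is specified. Applying the stated definition literally gives FRC extension patients up to 367 days and controls 185 to 191. For classes with little baseline use the apparent ratio is about 1.6 to 1.9 in favour of more medication in FRC, with no true difference. For classes already common at baseline it is close to 1.

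The direction follows from the definition for any positive start rate that is equal in the two arms. The size rests on assumed start rates, a constant rate, 200 to 230 patients entering the extension and no early stopping.

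No endpoint, model or hypothesis test uses this table. The primary result, power and type I error are unaffected. What is at risk is a misleading between-arm comparison of co-medication.

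**What to change.** In SAP 2.1.2 and 2.4.2, state that the between-arm concomitant table ends at the earlier of two points: the existing 3- or 9-day limit, and V28 (Day 183 if V28 is missing). Apply this to both arms. The V28/Day 183 cut-off is already used for extension-eligible patients in SAP 2.1.3 and 2.1.4, so no new rule or data collection is needed. Present whole-study concomitant medications in a separate table for FRC only, as SAP 2.4.3.1 does for exposure. If Appendix C already states a 26-week period, carry it into 2.4.2 so that the sections agree.

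The cost is one sentence and one extra table. Medications started in the extension would then appear only in the FRC table.

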2.4.3 Extent of investigational medicinal product exposure and compliance

The extent of IMP exposure and compliance will be assessed and summarized by actual treatment received within the safety population ([Section 2.3.2](#)).

2.4.3.1 Extent of investigational medicinal product exposure

The extent of open-label IMP exposure will be assessed by the duration of IMP exposure during the study.

The duration of treatment exposure will be the total number of days of administration of the open-label IMP, regardless of unplanned intermittent discontinuations.

The duration of daily IMP exposure will be calculated as:

(Date of the last open-label IMP injection – Date of the first open-label IMP injection) + 1.

The duration of weekly IMP exposure will be calculated as:

(Date of the last open-label IMP injection – Date of the first open-label IMP injection) + 7.

Duration of IMP exposure (days) will be summarized using continuous descriptive statistics (N, mean, SD, minimum, median, and maximum). The cumulative exposure in patient years, defined as the sum of patients' duration of IMP exposure, will also be provided. In addition, duration of IMP exposure will be summarized categorically by counts and percentages for each of the following categories, and cumulatively according to these categories:

- 1 to 14 days,
 - 15 to 28 days,
 - 29 to 56 days,
 - 57 to 84 days,
 - 85 to 126 days,
 - 127 to 168 days,
 - 169 to 182 days,
 - 183 to 210 days,
 - 211 to 238 days,
 - 239 to 294 days,
 - 295 to 364 days
 - > 364 days.
- The exposure parameters are provided for the 26-week randomized treatment period and for the whole study treatment period (FRC group only), respectively.

2.4.3.2 Compliance

Overall treatment compliance is defined as the actual number of days with IMP injection compared to the planned number of days with IMP injection during the open-label treatment period, up to treatment discontinuation. It is calculated according to the following formula:

- For QD/BID formulations,

$$\text{Compliance rate (\%)} = \left[\frac{\text{Total number of days with IMP injection}}{\text{Planned number of days with IMP injection}} \right] \times 100$$

- For QW formulations,

$$\text{Compliance rate (\%)} = \left[\frac{\text{Total number of weeks with IMP injection}}{\text{Planned number of weeks with IMP injection}} \right] \times 100$$

Treatment compliance will be summarized by treatment group using continuous descriptive statistics (N, mean, SD, median, and minimum, and maximum). In addition, the percentage of patients who have <60%, ≥60% to <80%, ≥80% to ≤100%, and >100% compliance will be summarized by treatment group.

The compliance parameters are provided for the 26-week randomized treatment period and for the 26-week single-arm extension period (FRC group only), respectively.

For calculating compliance rate during the 26-week single-arm extension period, the following formula will be used.

$$\text{Compliance rate (\%)} = \left[\frac{\text{Total number of days with IMP injection during extension period}}{\text{Planned number of days with IMP injection during extension period}} \right] \times 100$$

Date of the first IMP injection during extension period is equal to the date of first IMP administration with a daily dose > 0 after the date of administration reported on the eCRF “Treatment Status” page.

Cases of overdose (see study protocol for further details) will constitute AEs and be analyzed as such. More generally, dosing irregularities will be listed in [Section 2.2.1](#).

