8.1.3 Dose schedule

Insulin glargine/lixisenatide fixed ratio combination (FRC)

The FRC should be self-administered once daily in the morning in the hour (0 to 60 minutes) before breakfast, using Peach Pen or Olive Pen depending on the daily dose of insulin glargine.

Victoza®

Liraglutide (Victoza®) will be administered as per local labelling (such as SmPC in the European Union or PI in the US), continuing the same dose schedule as before randomization. Victoza® can be administered once daily at any time of day, independently of meals.

Byetta®

Exenatide BID (Byetta®) will be administered as per local labelling (such as SmPC in the European Union or PI in the US), continuing the same dose schedule as before randomization. Byetta® can be administered twice daily at any time within the 60 minute period before the morning and evening meal (or two main meals of the day, approximately 6 hours or more apart). Byetta® should not be administered after a meal.

At days of on-site visits, the IMP which is to be administered before breakfast should be self-administered at the investigational site under the observation of site staff.

Bydureon®

Exenatide extended-release (Bydureon®) will be administered as per local labelling (such as SmPC in the European Union or PI in the US), continuing the same dose schedule as before randomization. Bydureon® can be administered once a week at any time of day, independently of meals.

Tanzeum®

Albiglutide (Tanzeum®) will be administered as per local labelling (such as SmPC in the European Union or PI in the US), continuing the same dose schedule as before randomization. Tanzeum® can be administered once a week at any time of day, independently of meals.

Trulicity®

Dulaglutide (Trulicity®) will be administered as per local labelling (such as SmPC in the European Union or PI in the US), continuing the same dose schedule as before randomization. Trulicity® can be administered once a week at any time of day, independently of meals.

Injection site

The IMP should be administered by deep subcutaneous injection, alternating between the left and right anterolateral and left and right posterolateral abdominal wall or thighs or upper arms. Within a given area, location should be changed (rotated) at each time to prevent injection site skin reactions

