The use of balance scales is recommended; if digital scales are used, testing with standard weights is of particular importance. The floor surface on which the scale rests must be hard and should not be carpeted or covered with other soft material. The scale should be balanced with both weights at zero and the balance bar aligned. The patient should stand in the center of the platform as standing off-center may affect measurement. The weights are moved until the beam balances (the arrows are aligned). The weight is read and recorded in the e-CRF and Source Data. Self-reported weights are not acceptable; patients must not read the scales themselves.

9.2.1.2.5 *Dose of IMP*

The patients document daily/weekly their IMP dose(s) or any missed IMP injection(s) in the patient diary.

The following values will be entered in the e-CRF:

- GLP-1 RA (Victoza®, Byetta®, Bydureon®, Tanzeum®, or Trulicity®):
 - During the screening period and at randomization (V3): daily/weekly dose(s);
 - Throughout the treatment period (after V3 until V28): Any dose change(s).
- FRC:
 - From V3 to V19: daily dose and time of injection before breakfast on the day prior to each on site or phone visit;
 - After V19 and during extension period: daily dose. Time of injection to be recorded in case of change of dose;
 - Dose and time of injection on the day prior to PK sampling;
 - Dose and time of injection for any occurrence of hypoglycemia or allergic reaction;
 - Daily dose and time of injection used on the 7-point SMPG days, meal test days, and days of first and last injection of IMP.
- Missed IMP injections and overdose (if applicable);
- In case of any change in doses administered or hypoglycemia (if appropriate), the dose and injection time should be entered in the e-CRF.

9.2.1.2.6 *Fasting plasma glucose*

FPG is measured at a central laboratory. At V2, V28 and V35, FPG will be part of the standardized meal test.

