11.4.3.2 Compliance

Overall treatment compliance is defined as the actual number of days with IMP injection compared to the planned number of days with IMP injection during the open-label treatment period, up to treatment discontinuation. It is calculated according to the following formula:

For once/twice daily formulation

$$\text{Compliance rate (\%)} = \left[\frac{\text{Total number of days with IMP injection}}{\text{Planned number of days with IMP injection}} \right] \times 100 .$$

For once weekly formulations,

$$\text{Compliance rate (\%)} = \left[\frac{\text{Total number of weeks with IMP injection}}{\text{Planned number of weeks with IMP injection}} \right] \times 100$$

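### The day-based compliance rate counts a day with one of two exenatide BID doses in full, so it can overstate compliance for that part of the control arm

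*SAP*

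**What the plan says.** SAP 2.4.3.2 defines the rate in days: "Overall treatment compliance is defined as the actual number of days with IMP injection compared to the planned number of days with IMP injection". Under the label "For QD/BID formulations" it gives one formula, whose numerator is "Total number of days with IMP injection" and whose denominator is the planned number of such days. Protocol 11.4.3.2 has the same formula under "For once/twice daily formulation". Weekly products have their own version, in weeks.

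The dosing frequencies are in Protocol 8.1.3. For exenatide BID, "Byetta® can be administered twice daily at any time within the 60 minute period before the morning and evening meal". For the combination, "The FRC should be self-administered once daily in the morning in the hour (0 to 60 minutes) before breakfast". Liraglutide is also once daily, and the other three control drugs are once weekly.

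Neither document says what makes a day count for a twice-daily product, and neither gives a rate based on doses. The rate is summarized by arm in the safety population (SAP 2.4.3), as a continuous variable and in four classes cut at 60%, 80% and 100%.

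**The concern.** For the combination, liraglutide and the weekly products, the unit counted (day or week) holds exactly one planned injection, so the formula measures doses. Exenatide BID is the only product given more often than it is counted. On the natural reading, a missed dose leaves the rate unchanged whenever the other dose of that day was taken. The error can only raise the rate, and only in the control arm, so the two arms' rates are not fully like for like.

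The trial is open-label and compares the combination with continuation of the patient's existing drug. Readers will look at this table to see whether the comparator was taken as planned. SAP 1.5 records that Amendment 1 adapted the formula to weekly dosing; the twice-daily product stayed with the once-daily ones.

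No other planned summary clearly fills the gap. Exposure (SAP 2.4.3.1) runs from first to last injection and ignores interruptions. SAP 2.4.3.2 points to Section 2.2.1 for dosing irregularities, but that section deals with randomization and kit dispensing.

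**Working it through.** The plan states no compliance figure, so there is none to reproduce. The check applies the SAP formula to defined patterns of omission.

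**Inputs**
- Planned days D = 26 weeks × 7 = 182 (the full randomized period; the percentages do not depend on D).
- Planned exenatide BID injections = 2 × 182 = 364 (Protocol 8.1.3).
- Natural reading: a day counts if at least one injection was given.

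**General relation.** Let x₂, x₁ and x₀ be the days with two, one and no injections.
- SAP rate = (x₁ + x₂) / D
- Dose-based rate = (x₁ + 2x₂) / 2D
- Difference = x₁ / 2D

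The overstatement is half the proportion of days with exactly one injection. It is never negative, and it is zero when doses are missed only in whole days.

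**A patient who omits half of all doses** (dose-based rate 182/364 = 50%)

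| Pattern | SAP rate | Gap (points) |
|---|---|---|
| Both doses missed on alternate days | 91/182 = 50% | 0 |
| Doses missed independently at random | 1 − 0.5² = 75% (expected) | 25 |
| One dose missed every day | 182/182 = 100% | 50 |

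**Higher adherence, random misses.** With dose adherence a, the expected SAP rate is 1 − (1 − a)².

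| a | SAP rate | Gap (points) |
|---|---|---|
| 80% | 1 − 0.2² = 96% | 16 |
| 90% | 1 − 0.1² = 99% | 9 |
| 95% | 1 − 0.05² = 99.75% | 4.75 |

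**Planned classes, random misses.** The SAP rate reaches 80% when (1 − a)² ≤ 0.2, that is from a of about 55%. It falls below 60% only when (1 − a)² > 0.4, that is for a below about 37%.

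**Arm level.** The control mean is overstated by the exenatide BID share times the gap in those patients. The share is not in the documents, so the values below are assumptions.

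| Assumed share | a = 90%, random | a = 80%, random | Half omitted, one every day |
|---|---|---|---|
| 5% | 0.45 | 0.8 | 2.5 |
| 10% | 0.9 | 1.6 | 5 |
| 25% | 2.25 | 4.0 | 12.5 |
| 50% | 4.5 | 8.0 | 25 |

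**The case against.** The strongest reply is that nothing inferential depends on this rate. That stands. The mITT population is defined without regard to compliance (SAP 2.3.1.1). The primary MMRM uses all scheduled HbA1c values, including those after discontinuation or rescue (SAP 2.4.4.1). No per-protocol set or compliance covariate is planned.

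Second, the counting rule for a BID day is undefined, so the sponsor may intend that both injections are needed. The text does not exclude this, but it does not say so either, and the plain wording points the other way. Two programmers could produce different tables.

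Third, missed doses are recorded elsewhere: in the diary and e-CRF (Protocol 9.2.1.2.3.2 and 9.2.1.2.5), and through checks of returned pens (Protocol 8.7.1). Major deviations are also tabulated (SAP 2.2). So under-dosing is not hidden from the trial's records. None of these sources is planned to yield a dose-level rate, however.

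Three stronger readings are tempting and are not supported:
- A reader might infer that anyone omitting half the doses scores 100%. That needs exactly one miss every day.
- A reader might infer that compliance of the control arm as a whole is materially overstated. Only one of five control drugs is twice daily, each is supplied only where available in the country, and the share is not given.
- A reader might infer that the class above 100% can never be reached. Planned days are not defined, so this cannot be established.

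**Conclusion.** The point holds as a minor flaw in one descriptive table. On the natural reading, the formula cannot register a single missed exenatide BID dose on a day when the other was taken, and it can only err upward. Within affected patients the gap can be large: 9 points at 90% adherence and 16 points at 80% with random misses, and at most 50 points. Across the control arm it is that gap scaled by an unknown share, 0.9 points in the 10% and 90% example.

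These sizes rest on three assumptions: that a day with one injection counts, that misses within a day are independent where so stated, and that the share is as assumed. If misses come mainly as whole days, the overstatement shrinks towards zero. The primary comparison is unaffected in every case.

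**What to change.** In SAP 2.4.3.2 and Protocol 11.4.3.2, separate BID from QD. For BID products, define compliance as injections taken / (2 × planned days), taking missed injections from the e-CRF entries listed in Protocol 9.2.1.2.5. Keep the QD and QW formulas as they are.

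The documents do not show whether those entries separate one missed dose from a missed day. If they do not, count a BID day as compliant only when the diary records both injections, and say so in the SAP. This fallback is stricter. It gives x₂ / D, which lies below the dose-based rate by x₁ / 2D, the same amount by which the current formula lies above it. It also needs the diary injection records to be available for analysis.

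The cost is a line of text in each document and a short derivation. The downsides are reliance on how well missed injections are recorded, and a slightly lower reported compliance in the control arm.
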